## 3.5 Demographics and Pre-Treatment Characteristics

Subject demographics and pre-treatment characteristics will be summarized for the ITT analysis population, and some of these summaries may also be done for other populations when deemed important.

## 3.5.1 Demographics

The summary of demographics and subject characteristics will include age, race, ethnicity, education level, marital status, relationship status, how long the subject has been in her relationship, height, weight and body mass index (BMI) at baseline (from vital signs CRF), as well as uterine length (from pelvic exam CRF). The summary will be done for ITT, EP, ECYC, and include:

- The 6-number summary statistics (number of non-missing observations, mean, median, SD, minimum, and maximum) for age, height, baseline weight, baseline body mass index (BMI), and uterine length. Age will be calculated (with the INTCK function in SAS®) using the Screening Visit Date and the Date of Birth. Weight at baseline will be used for the summary.
- The number and percentage of subjects for categorical data, such as race, ethnicity, education level, parity (parous (≥1 birth) and nulliparous (not given birth)) marital status, relationship status, time (duration) of relationship, as well as the category of BMI: Underweight (< 18.5), Normal (18.5 24.9), Overweight (25.0 29.9), and Obese (≥ 30.0).

## 3.5.2 Medical History

Medical history data will be summarized by body system (Allergies, Heart, Digestive, Thyroid, etc.), as those reported on the CRF, for status of

- Ongoing
- Any (includes medical histories that are ongoing or resolved)

The number and percentage of subjects in each status will be provided by body system for the ITT population. If a subject reports more than one history/condition in the same body system, that subject will be counted only once for the summary of that body system.

## 3.5.3 Gynecological History

Gynecological history data will be summarized for the all questions collected on the CRF as follows:

- Does the subject currently use birth control method?
- Used/taken any of the following within the last 30 days: Clotrimazole, Monistat, Azo, Monistat, Tioconazole, or anything similar?
- Menstrual Characteristics (Menstrual Cycle, Had 3 consecutive periods?)
- How often, Average length, Usual flow; number and Percentage women outside normal range
- Usual level of discomfort caused by cramping and other discomforts
- Spotting between periods
- Sexually Transmitted Diseases (Any history STDs? History of Gonorrhea? History of Chlamydia?)
- PAP smear (Had a normal PAP or ASC-US with negative high risk HPV test result within the appropriate screening timeframe?)
- Were the results of the PAP Normal?
- Number of live births (Natural) and number of live births (C-Section)
- Still breastfeeding?
- Had two consecutive menses since last delivery?
- Any daily discomfort that can be attributed to gynecological issues (nonmenstrual)?
- If any, what is the level of this daily discomfort?

The number and percentage of subjects will be provided for each response to the question for categorical data, and 6-number statistics for continuous data.

## 3.5.4 Gynecological Examination

Gynecological examination will be performed during the screening visit and/or the date of VeraCept placement (before the procedure) in the following areas, and the results at the last assessment before the device placement will be summarized categorically.

- Vulva (Normal, Abnormal)
- Vaginal (Normal, Abnormal)
- Cervix (Normal, Abnormal)
- Adnexae (Normal, Abnormal)
- Uterus (Normal, Abnormal)
- Uterine irregularities found? (Yes, No)

#### 3.5.5 Prior Medications

All medications taken by the subject pre-trial and during the study will be recorded on the prior and concomitant medication CRF page. Prior medications are medications that were

taken before the study device VeraCept placement, and concomitant medications are medications taken on or after the placement. A medication may be both "prior" and "concomitant" if the subject took it before the placement and continued taking it during the study. See section 3.6 for more details on concomitant medications.

All medications recorded on the CRF will be coded to the therapeutic drug classes and generic drug names using the World Health Organization (WHO) Drug Dictionary, March 2014 version. The number and percentage of subjects who had prior medications that were coded to each generic drug name and therapeutic drug class, as well as the number and percentage of subjects who had at least one prior medication will be presented. Subjects reporting more than one drug in each drug class/generic name are only counted once to that drug class/generic name.

A table with number and percentage of subjects with pain medication use prior to VeraCept IUD insertion will be provided. A list of medications used by subjects who failed the insertion procedure will also be presented.

#### 3.6 Concomitant Medications

As defined in the Section 3.5.5, concomitant medications are medications taken on or after VeraCept placement. Similar to prior medications, concomitant medications will be summarized for Safety populations by the number and percentage of subjects in each coded drug name and drug class.

Another summary table will be presented for medications taken both before the study start and during the study.

## 3.7 Efficacy Analyses

## 3.7.1 Efficacy Analyses for Year 1 Data

Primary efficacy analysis was performed for the first year of the study (through Day 364) for Evaluable for Pregnancy population, by using Pearl Index. Pearl Index is defined as the number of pregnancies in 100 woman-years of method use. Pearl Index was calculated in subjects aged 18-35 at the time of VeraCept placement through the date of VeraCept removal or pregnancy, excluding the following cycles, unless the subject became pregnant in that cycle:

- When back-up contraception use was documented on the daily diary
- When the subject had no intercourse.

The Pearl Index formula is:

$$r = \frac{n}{L} \times 1300 = \frac{\text{Number of pregnancies}}{\text{Number of woman-cycles of pregnancy-risk}} \times 1300$$

where n is the number of pregnancies, and L is the number of woman-cycles, i.e., sum of the number of cycles each woman used the VeraCept up to and including the cycle of conception or until the time of VeraCept removal/expulsion, whichever comes earlier. The cycles of pregnancy-risk will be calculated as (Date of VeraCept removal/expulsion – Date of VeraCept placement + 1) / 28 for women who are not pregnant, and as (Date of pregnancy – Date of VeraCept placement + 1) / 28 for women who became pregnant

during the study. On-treatment pregnancies are defined to be pregnancies for which the estimated date of conception was within 7 days after study device expulsion or removal (the earlier of expulsion and removal dates will be used). The last cycle of pregnancy-risk can be a partial cycle and the partial cycle at risk is determined by dividing the number of days at risk in the cycle by 28 (e.g., 14/28 = 0.5 cycle of risk). If a cycle has a day with no information about backup contraception, that cycle will be excluded from the analysis (unless the subject became pregnant in that cycle).

To get the confidence interval (CI) for the Pearl Index, first the CI for the n (number of pregnancies) will be approximated by Poisson distribution sample mean's CI as

$$(\frac{\chi^{2}(\alpha/2;2n)}{2},\frac{\chi^{2}(1-\alpha/2;2n+2)}{2})$$

where  $\chi^2(\alpha/2;2n)$  in the lower limit is the Chi-square distribution (degrees of freedom = 2n) percentile with lower tail area (probability)  $\alpha/2$ , and  $\chi^2(1-\alpha/2;2n+2)$  in the upper limit is similarly defined. If n = 0, the lower limit will be set as 0.

Then the 95% CI for Pearl Index will be estimated as follows by set  $\alpha = 0.05$ .

( 
$$\frac{\chi^2(\alpha/2;2n)}{2}$$
 / L x 1300,  $\frac{\chi^2(1-\alpha/2;2n+2)}{2}$  / L x 1300 )

The summary table will present the number of subjects in the EP analysis population, number of pregnancies and the number of cycles of risk in addition to the Pearl Index and its 95% CI, for the following 3 scenarios:

- All EP subjects
- EP subjects with at least one live birth
- EP subjects never had live birth

Life-Table (Kaplan-Meier) method will also be used to present probabilities of pregnancy through 1-year (13 cycles) interval (through Day 364). The Evaluable for Pregnancy population will be used for the analysis and cycles will be compressed to provide contiguous cycles.

All efficacy analyses will be first done for all EP population, and then done by parity for 2 sub-groups of EP population: one sub-group subjects who had live child birth, and the other sub-group subjects who had not.

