Effectiveness will be evaluated as the absence of pregnancy during VeraCept use for up to12 months. Pregnancies judged to have occurred during study device use (determined by ultrasound and medical assessments), for which the estimated date of conception was within 7 days after study device removal or calculated date of expulsion, will be included in the per protocol analysis of pregnancies.

The Pearl Index (and 95% confidence intervals) will be calculated through 12 months for cycles in subjects aged 18-35 at the time of study device placement, excluding the following cycles (unless the subject became pregnant in the cycle):

- When back-up contraceptive or emergency contraceptive use was documented on the daily diary
- When the subject denied having any intercourse.

All pregnancies will be counted in the intent to treat analysis.

Life table analyses will be used as further assessment of pregnancies. Secondarily the Pearl index and life table analyses will be done through 3 years.

Safety and Other Outcome Measures

VeraCept ease of placement, removal and placement success will be descriptively summarized.

Safety evaluations will be based on the incidence of adverse events and serious adverse events changes from baseline in other assessments (examinations and vital signs) and by relationship to the study device or study device placement procedure. Study device tolerability will be based on changes in bleeding and spotting patterns and study discontinuation (including reasons for discontinuation).

Safety analyses will be based on the experience of all subjects who had attempted study device placement and provided any relevant data. Tolerability analyses will be based on the experience of all subjects who received a study device and provided any relevant data.

Subjects will record frequency and intensity of vaginal bleeding through a daily diary. The number of bleeding or spotting days will be summarized for each cycle. In addition, bleeding and spotting will each be summarized separately. Bleeding analyses will include all subjects who had a study device placed and have at least 1 cycle where they were not pregnant and were providing bleeding-related diary data on the days in the reference period.

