12.7 Emergency Contraception

If the subject suspects the VeraCept has expelled, she should contact the study site. Emergency contraception may be administered, according to product labelling, if the subject suspects expulsion has occurred and an act of intercourse might be unprotected, and she does not want the risk of pregnancy. If the subject is subsequently found to have an *in situ* IUD and desires to continue in the study, the cycle during which she used EC will not be included in the analysis unless the subject conceives. If the IUD is expelled, she will be exited from the study.

13. Diaries

Subjects will be instructed to complete diaries daily. Diaries are designed to collect the following information for each day of each menstrual cycle:

- Day of cycle
- Date
- Absence or presence of menstrual or other bleeding (none, spotting, normal or heavy)
- VeraCept expulsion (yes, no, suspected)
- Usage of additional birth control methods and type of birth control used
- Presence of abnormal pain or cramping
- Other medical problems
- All medications taken that day
- Frequency of intercourse
- Liner, pad and tampon usage

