20.6 Primary Outcome

The primary outcome measure is effectiveness and will be evaluated as absence of pregnancy during VeraCept use for up to 12 months. Pregnancies judged to have occurred while a study device was in place (determined by ultrasound and medical assessments) will be included in the analysis of pregnancies.

For the primary evaluation of effectiveness, the Pearl index (and 95% confidence intervals) will be calculated through 12 months for cycles in subjects aged 18-35 at the time of VeraCept placement, excluding the following (unless the subject became pregnant in the cycle):

- Cycles where back-up contraception use was documented on the daily diary
- Cycles with no intercourse.
- Cycles in which emergency contraception was used

The EP population will be used for the primary evaluation of effectiveness.

Life table analyses will be used as further assessment of pregnancies. Secondarily the Pearl index and life table analyses will be done through 3 years.

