## 3.4 Analysis Populations

All Screened: all subjects who signed Consent Form and screened at the study sites.

Intent To Treat (ITT): All subjects who underwent the study device placement procedure, regardless of whether the study device was successfully placed or not.

Safety: ITT subjects who had the device successfully placed.

Extension: ITT subjects who agreed to continue study device use after 12 months, up to 2 additional years for a total maximum of 3 years.

Evaluable for Pregnancy (EP): ITT subjects who had VeraCept placed successfully, and must meet both requirements 1 and 2 to be EP. Subjects must also meet either requirement 3 or requirement 4 to be EP.

1. between 18 to 35 years of age (inclusive) at enrollment

2. at least one report of pregnancy status after being enrolled

AND

3. have at least 1 cycle of diary with intercourse and without any backup contraception or emergency contraception (EC)

OR

4. have an on-treatment pregnancy, which is defined as the estimated conception date being on or after the insertion date and no more than 7 days after the VeraCept is removed or expelled.

Evaluable for Cycle Control (ECYC): ITT subjects with at least one cycle for which:

- A) a pregnancy did not occur; AND
- B) there was an assessment of bleeding in the diary data; AND
- C) the cycle has 14 or more days data.

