## 3.7.2 Efficacy Analyses for the Whole Study

Post-Year 1 sexual activity and contraceptive use information can be found in the Cycle Contact CRF, which was added since the Extension study (Year 2) started, i.e., this CRF wasn't present from the beginning of the study, but added as a mid-study change. Each record in this form is for one cycle and has the following 2 key questions for determining if a cycle is pregnancy-risk or not:

- Did the subject have intercourse at least once during the cycle? (Yes, No)
- Did the subject use backup contraception during the cycle? (Yes, No)

If the answer is "Yes" to the first question and "No" to the second question, or the subject was pregnant within a cycle (determined form the Pregnancy Test form), that cycle will be considered as a pregnancy-risk cycle; otherwise, the cycle will not be considered as a pregnancy-risk cycle.

For cycles without any Cycle Contact information, e.g., neither of the above 2 "Yes"/"No" questions were answered and a subject wasn't pregnant within the cycle either, the following procedure will be used to do the estimate for the subject:

- A. find the total number of such type of cycles for that subject
- B. find proportion of pregnancy-risk cycles from Year 1 diary data of the subject, which will be calculated as the number of pregnancy-risk cycles divided by the total number of cycles from Diary CRF
- C. The number from Step A is multiplied by the number from Step B, and then rounded to 1 decimal place, which will be the estimated number of pregnancy-risk cycles where Cycle Contact information is missing for the subject.

The number from Step C will be added to the number of pregnancy-risk cycles from those without missing Cycle Contact information, and then added to the Year 1 pregnancy-risk cycles from Diary CRF data to get denominator value of the Pearl Index for Year 2 (data cut off at 26 cycles) and Year 3 (data cut off at 39 cycles). The numerator will be the number of on-treatment pregnancies by the end of Cycle 26 and Cycle 39, respectively.

The Year 2 and Year 3 analyses will also be performed without inclusion of cycles with missing Cycle Contact information, i.e., not doing estimates of pregnancy-risk through the above Steps A, B, and C.

The 95% Confidence Intervals for the Pearl Index will be calculated, by using the formula in the above Section 3.7.1, at the following 3 scenarios:

- All EP subjects
- EP subjects with at least one live birth

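### SAP 3.7.1 leaves out the protocol's exclusion of emergency-contraception cycles from the primary Pearl Index, and no document says whether such cycles were removed as back-up

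*SAP*

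**What the plan says.** **Protocol.** EC cycles are excluded, unless the subject conceives, in three places.

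- Synopsis, Statistical Methods, Effectiveness Outcome: "When back-up contraceptive or emergency contraceptive use was documented on the daily diary".
- Section 12.7, for a woman who took EC, was then found to have the device in situ and continues: "the cycle during which she used EC will not be included in the analysis unless the subject conceives".
- Section 20.6, as a third item beside back-up use and no intercourse: "Cycles in which emergency contraception was used".

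The opening of section 20 says that the SAP is to follow the methods set out there.

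**SAP.** Section 3.7.1 has two exclusions for the primary Pearl Index, "When back-up contraception use was documented on the daily diary" and "When the subject had no intercourse", with an exception for cycles in which the subject became pregnant. It also drops any cycle that has a day without backup information. EC is not mentioned. Outside the abbreviation list, EC appears only in the Evaluable for Pregnancy (EP) definition of section 3.4, where requirement 3 is to "have at least 1 cycle of diary with intercourse and without any backup contraception or emergency contraception (EC"). For Years 2 and 3, section 3.7.2 classifies a cycle by whether intercourse took place and by one further question: "Did the subject use backup contraception during the cycle? (Yes, No").

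**The concern.** The primary denominator rule in the SAP is not the protocol's, and the SAP gives no reason for the change. EP requirement 3 does not close the gap. It decides whether a woman enters the population, not which of her cycles count. Once she has one cycle with intercourse and neither backup nor EC, nothing in SAP 3.7.1 removes her EC cycles from L.

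The direction is one-sided. A cycle in which she conceives is kept under both rules. The cycles on which the rules differ are therefore all non-pregnant, and keeping them can only favour the device.

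The rule also reaches past Year 1. Under SAP 3.7.2, Year 1 risk cycles are added to the Year 2 and Year 3 denominators, and each woman's Year 1 risk-cycle proportion (Step B) is used to estimate her cycles without Cycle Contact data. The Year 1 life table, which compresses cycles, is affected too if it uses the same cycle filter.

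**Working it through.** **The rules side by side, for a cycle with intercourse, EC use, no back-up recorded and no conception**

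| Rule | Cycle in L? |
|---|---|
| Protocol synopsis, 12.7 and 20.6 | No |
| SAP 3.7.1 as written | Yes |
| SAP 3.7.1 if EC was coded as back-up | No |
| SAP 3.7.2 as written | Yes |

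**Inputs.** From the protocol's sample-size text: 225 subjects aged 18-35, 10 cycles each on average, 1% without diary data, 9.2% of cycles lost to no intercourse or backup, 2,015 evaluable cycles, one pregnancy, Pearl Index 0.6. From SAP 3.7.1: Pearl Index = n/L × 1300, with exact Poisson limits from the chi-square distribution.

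**Reproducing the plan's figures.** 225 × 0.99 × 10 × (1 − 0.092) = 2,022.6; with 222 whole subjects, 222 × 10 × 0.908 = 2,015.8. Both are close to 2,015. The index is 1/2,015 × 1300 = 0.645, which rounds to the stated 0.6. The SAP's formula gives limits of 0.02 and 3.59. The plan states (0.1, 3.3); that difference is a separate matter and nothing here depends on it.

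**Effect of retained EC cycles.** The documents give no EC frequency, so the share is an assumption. Taking 2,015 as free of EC cycles and adding them, with one pregnancy:

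| Assumed EC cycles, % of 2,015 | L | Pearl Index | Upper 95% limit |
|---|---|---|---|
| 0 | 2,015 | 0.645 | 3.59 |
| 0.5 | 2,025 | 0.642 | 3.58 |
| 1 | 2,035 | 0.639 | 3.56 |
| 2 | 2,055 | 0.633 | 3.52 |
| 5 | 2,116 | 0.614 | 3.42 |

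One per cent is already about 20 cycles (0.01 × 2,015).

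**If 2,015 already contains EC cycles.** The 9.2% loss names only no intercourse and backup, so this is possible. Removing 1% gives L = 1,994.8, an index of 0.652 and an upper limit of 3.63. The relative change is again about 1%.

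**No pregnancies.** The index is 0 under either rule. The upper limit is −ln(0.025) × 1300/L: 3.689 × 1300/2,015 = 2.38, falling to 3.689 × 1300/2,035 = 2.36 with 1% extra cycles.

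**Carry-over into Years 2 and 3.** For a woman with 13 Year 1 diary cycles, one retained EC cycle raises her Step B proportion by 1/13 = 0.077. If all of her 39 − 13 = 26 later cycles lacked Cycle Contact data, Step C would add 26 × 1/13 = 2.0 cycles to the Year 3 denominator, besides the one carried over directly. That is the extreme case; with no missing contacts only the one cycle carries over.

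**The case against.** The best defence is that EC may already be handled as back-up. The diary (Protocol section 13) records "Usage of additional birth control methods and type of birth control used", the synopsis puts back-up and EC in one diary-based bullet, and the first SAP exclusion relies on the same diary. Usage is also loose elsewhere: the 9.2% assumption omits EC although the same synopsis excludes it. This stands as a possibility. A reader might therefore infer from the SAP that EC cycles were in fact counted in the completed Year 1 result; the documents do not show that. Nor do they state the mapping, and SAP 3.4 names the two as different things. Section 20's instruction to follow the protocol's methods is a reason to restore the exclusion, not to leave it implied.

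A second stronger reading is that these are cycles in which device protection is least certain, because EC follows suspected expulsion. Section 12.7 does not support it. The continuing cycles at issue are those in which the device was found in situ. A confirmed expulsion ends participation, and L stops there.

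The number of affected cycles is also limited. Section 4.6 tells a woman who suspects expulsion to abstain or use non-hormonal contraception until evaluated, so some of these cycles would already leave under the back-up exclusion.

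Finally, it can be said that the effect vanishes at one decimal. In the table every index rounds to 0.6, and at 1% the upper limit still rounds to 3.6. This shows that the effect is small, but the rounding is not a safe argument: at 2% the upper limit rounds to 3.5, and if 2,015 already contains EC cycles, removing 1% gives 0.652, which rounds to 0.7.

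**Conclusion.** The point holds as a conflict between protocol and SAP on the primary denominator. Followed as written, SAP 3.7.1 keeps EC cycles without conception that the protocol removes. Whether any were actually kept depends on coding that the documents do not describe.

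Any error lowers the Pearl Index, or only its upper limit when n = 0. Its size is about 1% of the index and of the upper limit per assumed 1% of cycles, and the true share is probably low because section 12.7 describes EC only for suspected expulsion. The figures assume one pregnancy and 2,015 cycles, and the EC shares are illustrative. The case rests on the departure from protocol and the one-way direction, not on a material change in the estimate.

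**What to change.** 1. Add a third exclusion to SAP 3.7.1, *When emergency contraception was used*, under the existing exception for cycles in which the subject became pregnant.
2. Confirm how EC was coded in the completed Year 1 programming. SAP 3.1.2 says that this analysis has been done. If any EC cycle was counted, rerun Year 1, because its cycles enter the Year 2 and Year 3 denominators and the Step B proportion. SAP 1.0 places this SAP before the final Year 2 and Year 3 analysis began.
3. In SAP 3.7.2, treat a cycle as backup = Yes when EC is reported at Cycle Contact or has a concomitant-medication record dated within that cycle. The protocol collects concomitant medications until study exit (sections 4.5 and 14). Do not use the long-term visit question on additional birth control (SAP 3.8.10): it covers six months and cannot be assigned to a 28-day cycle.

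The list in section 20.6 is for the 12-month index, and the later analyses are secondary, so item 3 is for consistency; section 12.7 sets no time limit on its exclusion. Cycle Contact has no separate EC question, so capture after Year 1 will be incomplete, and the SAP should say so.

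The cost is one bullet, one programming condition, and a check and possible rerun of Year 1. A few cycles may leave the denominator.

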## 2.4 Study Endpoints

## 2.4.1 Primary Endpoints

The primary outcome measure is study device effectiveness, evaluated as the absence of pregnancy up to 12 months (13 cycles of 28 days each) of VeraCept use.

Contraceptive failure rate will be calculated using the Pearl Index through 13 cycles. All evaluable cycles prior to discontinuation or planned removal at 12 months (13 cycles) will be included in the primary analysis of effectiveness. The calculation will be first done for all ("Total") subjects, and then for sub-groups of parous ("Parous") and nulliparous ("Nulliparous") women of child-bearing age.

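### SAP 3.7.1 gives a calendar-time formula for the primary Pearl Index denominator that contradicts its own cycle exclusions and Day 364 limit

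*SAP*

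**What the plan says.** SAP 3.7.1 describes the Year 1 denominator in several ways.

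- **Time limit:** "Primary efficacy analysis was performed for the first year of the study (through Day 364").
- **Exclusions:** the index is calculated "excluding the following cycles, unless the subject became pregnant in that cycle". The listed cycles are those with back-up contraception in the diary and those with no intercourse.
- **Definition of L in words:** "sum of the number of cycles each woman used the VeraCept up to and including the cycle of conception", or until removal or expulsion if earlier. This counts use, not risk, although the displayed ratio labels the denominator as woman-cycles of pregnancy risk.
- **Computing rule:** "The cycles of pregnancy-risk will be calculated as (Date of VeraCept removal/expulsion" minus the placement date, plus 1, divided by 28. For a woman who conceives, the pregnancy date replaces the removal date.
- **Further exclusion, stated after the rule:** "If a cycle has a day with no information about backup contraception, that cycle will be excluded from the analysis", unless she conceived in that cycle.

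SAP 2.4.1 supports the filtered version: "All evaluable cycles prior to discontinuation or planned removal at 12 months (13 cycles) will be included in the primary analysis of effectiveness". SAP 3.7.2 later adds "Year 1 pregnancy-risk cycles from Diary CRF data to get denominator value of the Pearl Index" for Years 2 and 3.

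**The concern.** The computing rule and the cycle rules cannot both set L. The rule is elapsed device time in 28-day units, and no sentence says to subtract the excluded cycles or to truncate at Day 364. Two programmers working from the same section could report different primary results.

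The rule also fails for women who continue after Week 52. At the Year 1 cut they have no removal date. By the end of the study they have one, possibly near three years, and the same rule would then return a different Year 1 value.

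This is the denominator of the primary endpoint. Keeping non-risk cycles always enlarges L, so that part of the discrepancy lowers the index and its confidence limits, in the device's favour.

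**Working it through.** **1. One woman (illustration).** Suppose the device is removed on Day 364 and one of the 13 cycles had back-up use. The formula gives 364/28 = 13 cycles; the exclusion rule gives 12. Removal at the end of the protocol's Week 52±2 window is Day 378, and the formula then gives 378/28 = 13.5, above the 13-cycle limit. Removal on Day 1095 gives 1095/28 = 39.1.

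**2. The plan's own figures.** The protocol's Sample Size section gives 225 women aged 18-35, an average of 10 cycles each, 1% without diary data, and 9.2% of cycles without intercourse or with back-up use.

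- At-risk cycles: 225 × 10 × 0.99 × 0.908 = 2,022.6, against 2,015 stated. This agrees within 0.4%.
- Pearl Index with one pregnancy: 1/2,015 × 1300 = 0.645, which matches the stated 0.6 after rounding.
- The stated interval (0.1, 3.3) does not follow from 2,015 cycles under the SAP's Poisson formula, which gives (0.02, 3.59). That is a separate matter. The comparison below uses the SAP formula throughout.

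**3. Exclusions kept or removed, within Year 1.** The upper limit for n = 1 is χ²(0.975; 4)/2 ÷ L × 1300, with χ²(0.975; 4)/2 = 5.5716.

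| Denominator | L | Pearl Index | Upper limit |
|---|---|---|---|
| Exclusions applied | 2,022.6 | 1300/2,022.6 = 0.643 | 3.58 |
| Calendar formula | 225 × 10 × 0.99 = 2,227.5 | 1300/2,227.5 = 0.584 | 3.25 |

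The ratio is 0.908, so the index and both limits are 9.2% too low. Starting from the stated 2,015 cycles (2,015/0.908 = 2,219) gives the same contrast: 0.645 (upper limit 3.59) against 0.586 (3.26).

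**4. Sensitivity to the excluded share (assumed values, from 2,015 at-risk cycles).** Literal use of the formula gives 0.613 if 5% of cycles are excluded, 0.548 if 15%, and 0.516 if 20%, each against 0.645. The planning 9.2% does not include cycles lost to missing back-up information, which would widen the gap. With no pregnancies the index is 0 either way and only the upper limit moves, from 2.38 to 2.16.

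**5. The missing cap.** Sizing it needs the share of women who keep the device after Week 52, which the documents do not give. The direction is not fixed either:

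- Late removal dates with Year 1 pregnancies only would enlarge L and lower the index.
- Dropping women who have no removal date would shrink L and raise it.
- Leaving the numerator uncapped as well would make the direction depend on the later pregnancy rate.

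**The case against.** The strongest reply is that the plan does contain both rules. The Day 364 limit and the exclusions stand in the same section as the formula, one exclusion is stated after it, and SAP 2.4.1 asks for evaluable cycles within 13 cycles. On this reading the formula only converts an interval to 28-day units, and the cycle rules then remove cycles.

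Other text fits that reading. The life-table paragraph in SAP 3.7.1 has cycles compressed to be contiguous, which presupposes that some were removed. SAP 3.7.2 takes the Year 1 count from the diary, and its Step B divides risk cycles by all diary cycles, which makes sense only if the former are a subset. Scheduled diary dispensing ends at Visit 5 and collection at Week 52, so the missing-information rule, if applied, would drop later cycles.

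This shows what was probably intended, and it stands to that extent: the plan does not omit the exclusions or the cap. It does not repair the formula, which is the only explicit calculation and carries neither. Nor does it supply an end date for women still using the device.

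It is also fair that the study is called exploratory and states no success threshold for the Pearl Index, so no pass/fail decision turns on this. At one decimal, 0.64 and 0.58 both print as 0.6; the upper limit shows the difference more clearly (3.6 against 3.3).

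**Conclusion.** SAP 3.7.1 contradicts itself on the primary denominator and needs correction. If the formula is programmed literally within Year 1, the index is about 9% too low: 0.58 (upper limit 3.25) instead of 0.64 (3.58) with one pregnancy. This rests on the protocol's planning inputs and on reading its 10 cycles per woman as cycles of use before the 9.2% is removed, which is how the protocol's own arithmetic works.

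Three stronger readings are tempting but not supported.

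- **That the reported primary failure rate is understated.** The Year 1 analysis was completed before this SAP, which builds on a Version 1.00 not available here. Nothing shows which denominator was run.
- **That the missing cap cuts the index by half or more.** If 50% of women each added 26 cycles with one pregnancy, the index would be about 0.25; at 10% it would be about 0.46. Both shares are assumptions, and nothing shows that late removal dates entered the Year 1 table.
- **That every departure favours the device.** This holds for retained non-risk cycles, but not for women without a removal date or for an uncapped numerator.

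**What to change.** Replace the computing sentence in SAP 3.7.1.

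- Define L as the sum over women of at-risk 28-day cycles in Days 1-364 (cycles 1-13), with the last cycle counted as a fraction.
- End each woman's time at the earliest of conception, removal, expulsion, last diary or contact, and Day 364.
- Subtract cycles with back-up use, no intercourse or missing back-up information, but keep a cycle in which she conceived.
- Apply the same Day 364 limit to the pregnancies in the numerator.
- Keep the calendar formula only for the exposure summary (SAP 3.8.1).
- State which denominator produced Table 14.2.1-Y1, and rerun it if the literal formula was used.
- Confirm that the Year 1 count carried into the Year 2 and Year 3 denominators, and into Step B of SAP 3.7.2, is the diary-based at-risk count. If the calendar count were used in Step B, the proportion would approach or exceed 1 and inflate the estimated cycles.

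The cost is an SAP wording change, minor reprogramming and a check of one table. If the literal formula was used within Year 1, the corrected index will be slightly less favourable.
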